8.4 Duration of Follow Up

After coming off study treatment, participants will be followed as per the local standard of care for brain imaging until removal from study or until death, whichever occurs first. Reference Section 12.3 for more information regarding follow up requirements.

8.5 Criteria for Removal from Study Drug

Participants will be removed from study when any of the criteria listed below or in section 6.9 applies. The reason for study removal and the date the participant was removed will be documented in the Case Report Form.

Treatment Discontinuation Criteria for Nivolumab

Nivolumab treatment should be permanently discontinued for the following:

- Any Grade 2 drug-related uveitis, eye pain, or blurred vision that does not respond to topical therapy and does not improve to Grade 1 severity OR requires systemic treatment
- Any Grade 3 non-skin, drug-related AE lasting > 7 days, with the following exceptions for laboratory abnormalities, drug-related uveitis, pneumonitis, bronchospasm, hypersensitivity reactions, infusion reactions, and endocrinopathies:
 - Grade 3 drug-related uveitis, pneumonitis, bronchospasm, hypersensitivity reaction, or infusion reaction of any duration requires discontinuation [SEP]
 - Grade 3 drug-related endocrinopathies adequately controlled with only physiologic hormone replacement do not require discontinuation [SEP]
 - Grade 3 drug-related laboratory abnormalities do not require treatment discontinuation except:
 - Grade 3 drug-related thrombocytopenia > 7 days or associated with bleeding requires discontinuation
 - Grade >3 drug-related AST, ALT, or TBILI requires discontinuation*
 - Concurrent AST or ALT > 3xULN and TBILI > 2xULN [SEP]

* In most cases of Grade 3 AST or ALT elevation, study drug(s) will be permanently discontinued. If the investigator determines a possible favorable benefit/risk ratio that warrants

continuation of study drug(s), a discussion between the principal investigator and the treating physician must occur.

- Any Grade 4 drug-related AE or laboratory abnormality, except for the following events which do not require discontinuation:
 - Grade 4 neutropenia \leq 7 days
 - Grade 4 lymphopenia or leukopenia
 - Isolated Grade 4 amylase or lipase abnormalities that are not associated with symptoms or clinical manifestations of pancreatitis
 - Isolated Grade 4 electrolyte imbalances/abnormalities that are not associated with clinical sequelae and are corrected with supplementation/appropriate management within 72 hours of their onset
 - Grade 4 drug-related endocrinopathy AEs, such as adrenal insufficiency, ACTH deficiency, hyper- or hypothyroidism, or glucose intolerance, which resolve or are adequately controlled with physiologic hormone replacement (corticosteroids, thyroid hormones) or glucose-controlling agents, respectively, may not require discontinuation after discussion with and approval from the principal investigator
- Any event that leads to delay in dosing lasting $>$ 8 weeks from the previous dose requires discontinuation, with the following exceptions:
 - Dosing delays to allow for prolonged steroid tapers to manage drug-related AEs are allowed. Tumor assessments should continue as per protocol even if dosing is delayed. Periodic study visits to assess safety and laboratory studies should also continue every 6 weeks or more frequently if clinically indicated during such dosing delays.
 - Dosing delays lasting $>$ 8 weeks from the previous dose that occur for non-drug-related reasons may be allowed if approved by the principal investigator. Prior to re-initiating treatment in a participant with a dosing delay lasting $>$ 8 weeks, the principal investigator must be consulted. Tumor assessments should continue as per protocol even if dosing is delayed. Periodic study visits to assess safety and laboratory studies should also continue every 6 weeks or more frequently if clinically indicated during such dosing delays.
- Any AE, laboratory abnormality, or intercurrent illness which, in the judgment of the investigator, presents a substantial clinical risk to the participant with continued nivolumab dosing

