6.9 Early Withdrawal of Subjects

When and How to Withdraw Subjects

Discontinuation of Subjects following any Treatment with Study Drug

Participants MUST discontinue investigational product (and non-investigational product at the discretion of the investigator) for any of the following reasons:

- Participant's request to stop study treatment
- Participant repetitive and significant non-compliance

- Disease progression, except as described in Section 13.3
- Unacceptable toxicity, see Section 8.5
- Any clinical AE, laboratory abnormality, or intercurrent illness which, in the opinion of the investigator, indicates that continued participation in the study is not in the best interest of the participant, see Section 8.5
- Pregnancy
- Termination of the study
- Loss of ability to freely provide consent through imprisonment or involuntarily incarceration for treatment of either a psychiatric or physical illness
- This study has a progression-free and overall survival endpoint; therefore participants discontinuing study treatment will remain on study for documentation of progression and death.

In the case of pregnancy, the investigator must immediately notify Sponsor or designee of this event. In most cases, the study drug(s) will be permanently discontinued in an appropriate manner. Please contact the Sponsor or designee within 24 hours of awareness of pregnancy. If the investigator determines a possible favorable benefit/risk ratio that warrants continuation of study drug, a discussion between the investigator and the Sponsor or designee must occur.

All participants who discontinue study drug should comply with protocol specified follow-up procedures as outlined in Section 12.3. The only exception to this requirement is when a participant withdraws consent for all study procedures including post-treatment study follow-up or loses the ability to consent freely (ie, is imprisoned or involuntarily incarcerated for the treatment of either a psychiatric or physical illness).

If study drug is discontinued prior to the participant's completion of the study, the reason for the discontinuation must be documented in the subject's medical records and entered on the appropriate case report form (CRF) page.

Data Collection and Follow-up for Withdrawn Participants

Post Study Drug Study Follow-up

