In this study, OS is a secondary endpoint. Post study follow-up is of critical importance and is essential to preserving subject safety and study integrity. Participants who discontinue study drug must continue to be followed every 3 months after the second off-nivolumab follow-up visit, for collection of outcome and/or survival follow-up data as required and in line with Section 12.3 until death or study conclusion. Survival follow-up may be accomplished by visit or phone contact.

Withdrawal of Consent

Participants who request to discontinue study drug will remain in the study and must continue to be followed for protocol specified follow-up procedures. The only exception to this is when a subject specifically withdraws consent for any further contact with him/her or persons previously authorized by participant to provide this information. Participants should notify the investigator of the decision to withdraw consent from future follow-up **in writing**, whenever possible. The withdrawal of consent should be explained in detail in the medical records by the investigator, as

to whether the withdrawal is from further treatment with study drug only or also from study procedures and/or post treatment study follow-up, and entered on the appropriate CRF page. In the event that vital status (whether the subject is alive or dead) is being measured, publicly available information should be used to determine vital status only as appropriately directed in accordance with local law.

Lost to Follow-Up

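### Section 8.5 removes participants from the study when they stop nivolumab, contradicting 6.9, 5.6 and 12.3; applied literally it would lose most OS events and some PFS and DOR events

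*Combined protocol and SAP*

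**What the plan says.** **Removal.** Section 8.5 is headed as criteria for removal from study drug, and its list gives conditions for permanently discontinuing nivolumab. Its opening sentence nevertheless reads: "Participants will be removed from study when any of the criteria listed below or in section 6.9 applies". The next sentence requires the reason for study removal and its date on the case report form.

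**Imaging follow-up.** Section 8.4 says that, once nivolumab has stopped, "participants will be followed as per the local standard of care for brain imaging until removal from study or until death, whichever occurs first". It then refers to 12.3 for follow-up requirements.

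**Staying on study.** The 6.9 list that 8.5 imports gives reasons for stopping investigational product, among them "Disease progression, except as described in Section 13.3". Its last entry says that "participants discontinuing study treatment will remain on study for documentation of progression and death". Section 6.9 adds: "Participants who request to discontinue study drug will remain in the study and must continue to be followed for protocol specified follow-up procedures". Follow-up is every 3 months, "until death or study conclusion. Survival follow-up may be accomplished by visit or phone contact". The exceptions in 6.9 are withdrawal of consent for further contact or follow-up and loss of the ability to consent freely. Loss to follow-up has its own procedure.

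**Supporting sections.** Section 5.6 and Table 12.3 continue scans after a stop for a reason other than progression, until progression or subsequent anti-cancer therapy. The note to Table 12.3 continues survival follow-up for all patients. Section 15.5 censors OS at the last date known alive.

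**The concern.** PFS, OS and DOR are the trial's secondary endpoints, and all three need observation after drug stop. Section 8.5 is where a site looks when a participant stops nivolumab, and there it is told to record removal from the study. Progression is one of the stopping criteria, so a literal reading ends observation at progression, before most deaths. It also ends observation at a stop for toxicity, request or non-compliance, before progression is seen. Those stops may be related to prognosis, so the resulting censoring could be informative. The trial has three sites and 37 planned participants, so a few exits coded this way would visibly change the OS curve.

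**Working it through.** **1. The plan's own figure.** The documents give no event count or power for PFS or OS. The only design figure is for ORR (15.2): 10% against 30%, one-sided alpha 0.05, power 0.90, 33 evaluable. With n = 33 and success at 7 or more responses, the exact binomial gives alpha 0.0417 and power 0.9056. Allowing for 10% unevaluable, 33/0.9 = 36.7, rounded up to 37. Both reproduce, and neither depends on the removal wording.

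**2. The rules side by side.**

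| Event | 8.5 and 8.4 read literally | 6.9, 5.6 and 12.3 |
|---|---|---|
| Stop for progression | Removed from study; later death not sought | Survival follow-up every 3 months until death or study conclusion |
| Stop for toxicity or non-compliance | Removed; imaging follow-up ends | Scans until progression or new therapy; survival follow-up |
| Stop at participant's request | Removed; imaging follow-up ends | Remains in study unless consent to follow-up or contact is withdrawn |

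Both columns cannot be followed, and no precedence is stated.

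**3. OS, simple calculation.** Assume exponential OS with median 10 months, the upper end of the 8 to 10 months that section 3 gives for recurrent high-grade glioma. Assume independent exponential time on drug with median m; m is not in the documents. The share of deaths occurring before drug stop is (1/10)/(1/10 + 1/m) = m/(m + 10).

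- m = 2: 2/12 = 17% seen, 83% lost.
- m = 4: 4/14 = 29% seen, 71% lost.
- m = 6: 6/16 = 37.5% seen, 62.5% lost.

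In this model the loss exceeds half whenever median time on drug is shorter than median OS.

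**4. OS and PFS, with progression as a stopping event.** A simulation over 36 months (the synopsis study duration, ignoring staggered entry) used these inputs:

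- median PFS of 3.2 months (13.9 weeks in the PD-L1 inhibitor study cited in section 3), 6 or 12 months;
- a share q of participants stopping for another reason before the PFS event, 5 to 30%;
- a share d of PFS events that are deaths without progression, 5 to 20%;
- median survival after progression of 6 months;
- completion of 2 years counted as removal or not, since it is not a listed criterion.

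Apart from the 13.9 weeks and the 36 months, these are assumptions.

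- *OS.* Only a death without progression and before any other stop is seen, so with complete follow-up the loss is about 1 − (1 − q)d. For q = 0.05 and d = 0.20 this is 1 − 0.95 × 0.20 = 81%. For q = 0.30 and d = 0.05 it is 1 − 0.70 × 0.05 = 96.5%. The simulated range is 73 to 96%. The lowest values arise with median PFS 12 months and completion not counted as removal. With median PFS 13.9 weeks and q of 5 to 10%, 29 to 34 of about 36 deaths are lost.
- *PFS.* Progression that stops drug is itself the PFS event and is recorded at removal. Only events after another kind of stop are lost, a share of about q. The simulated range is 3 to 30%, or 5 to 31% if completion counts as removal. With median PFS 13.9 weeks and q of 5 to 10%, that is about 2 to 4 of 37 events.
- *DOR.* The same gap exists for responders who stop before progressing. The documents give no basis for a figure.

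**The case against.** The strongest reply is that this is a slip of the pen that nobody would act on. The heading and list of 8.5 concern drug. The 6.9 list it imports contains the remain-on-study statement. Section 6.9 calls post-study follow-up critically important, and the two follow-up visits in 12.3 would have almost no one to attend them under a literal reading. Section 8.4 concerns brain imaging, treats coming off treatment and removal from study as different events, and points to 12.3. The OS censoring rule uses the last date known alive, not a removal date, and 12.3 lets the principal investigator request survival status on all treated participants unless they have withdrawn consent for all contact.

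Most of this stands. It makes a slip the likely explanation, and it means that 8.4 sets no end to survival follow-up and that some lost survival data could be recovered. It does not remove the conflict: 8.5 gives an instruction and a date to record, and a site that follows it stops seeking the information on which the last date known alive depends.

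A reader might also infer that most PFS events would be lost. The documents do not support that, because progression is both a stopping criterion and the PFS event. More than half of PFS events would be lost only if more than half of participants stopped for other reasons before progressing, and no such figure is given.

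The OS illustrations are rough. The 10-month median is for high-grade disease, whereas the trial also enrols grade 2 and only IDH-mutant tumours, which section 3 associates with longer survival. Treatment beyond progression, allowed in 11.2, would lower the loss somewhat.

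**Conclusion.** The contradiction is real, and 8.5 is wrong as written. The harm is conditional on a site applying it literally. In that case most OS events would be lost, roughly 60 to 95% across the two illustrations. PFS and DOR would lose only the events that follow a stop for a reason other than progression, about 3 to 31% of PFS events. These ranges show direction and order of size; time on drug, the share of non-progression stops, the share of deaths without progression and survival after progression are all assumed. The ORR sample size and decision rule are unaffected, and the endpoint definitions in 15.5 need no change. This should be corrected, because secondary endpoints are exposed to an avoidable loss and the correction is small.

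**What to change.** - **Section 8.5.** Change *removed from study* to *removed from study drug*, and *study removal* to *study drug discontinuation*. Record study exit as a separate date.
- **Section 8.4.** Replace *removal from study* by reference to the existing rules. Imaging follow-up ends as in 5.6 and 12.3, at progression or start of subsequent anti-cancer therapy. Survival follow-up ends as in 6.9, at death or study conclusion. Both are subject to the 6.9 provisions on withdrawal of consent for further contact, lost ability to consent freely, and loss to follow-up.

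A general clause ending all follow-up only at consent withdrawal, loss to follow-up or study conclusion would not do. It would clash with the imaging end points in 5.6 and 12.3 and would omit the 6.9 exception for lost ability to consent.

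The cost is a few sentences of protocol text and a check that the case report form holds the two dates separately; the form is not among the documents, so whether it already does is unknown. No visits are added, and no dose or drug-stopping criterion changes.

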9 DOSING DELAYS/DOSE MODIFICATIONS

Dose Modifications for Nivolumab

Dose modifications are not allowed for nivolumab.

Dose Delay Criteria for Nivolumab

Tumor assessments should continue per protocol schedule, even if dosing is delayed. Treatment delays will be recorded, but the total duration of therapy will be up to two years, regardless of the number of cycles. Nivolumab administration should be delayed for the following:

- Any Grade ≥ 2 non-skin, drug-related AE, with the following exception:
 - Grade 2 drug-related fatigue or laboratory abnormalities do not require a treatment delay
- Grade 2 drug-related creatinine, AST, ALT, or TBILI abnormalities
- Any Grade 3 skin, drug-related AE
- Any Grade 3 drug-related laboratory abnormality (excluding AST, ALT, or TBILI), with the following exceptions for lymphopenia or asymptomatic amylase or lipase:
 - Grade 3 lymphopenia does not require dose delay
 - Any Grade ≥ 3 drug-related amylase or lipase abnormality that is not associated with symptoms or clinical manifestations of pancreatitis does not require dose delay
- Any AE, laboratory abnormality, or intercurrent illness which, in the judgment of the investigator, warrants delaying the dose of study medication [L]
[SEP]

Participants who require delay of nivolumab should be re-evaluated weekly or more frequently if clinically indicated, and resume nivolumab dosing when re-treatment criteria are met.

Criteria to Resume Dosing for Nivolumab

Participants may resume treatment with study drug when the drug-related AE(s) resolve to Grade ≤ 1 or baseline value, with the following exceptions:

- Participants may resume treatment in the presence of Grade 2 fatigue.
- Participants who have not experienced a Grade 3 drug-related skin AE may resume treatment in the presence of Grade 2 skin toxicity.
- For participants with Grade 2 AST, ALT, or TBILI elevations, dosing may resume when laboratory values return to baseline and management with corticosteroids, if needed, is complete.
- Participants with combined Grade 2 AST/ALT AND TBILI values meeting discontinuation parameters should have treatment permanently discontinued.

Columbia University Medical Center
Herbert Irving Comprehensive Cancer Center
Version Date: January 30, 2024

- Drug-related pulmonary toxicity, diarrhea, or colitis must have resolved to baseline before treatment is resumed. Participants with persistent Grade 1 pneumonitis after completion of a steroid taper over at least 1 month may be eligible for retreatment.
- Participants with drug-related endocrinopathies adequately controlled with only physiologic hormone replacement may resume treatment after consultation with the principal investigator.

Recommended Dose Modifications for Nivolumab

Event	Severity*	Dose modification
Colitis	Grade 2 or 3 diarrhea or colitis	Withhold dose ^a
	Grade 4 diarrhea or colitis	Permanently discontinue
Pneumonitis	Grade 2 pneumonitis	Withhold dose ^a
	Grade 3 or 4 pneumonitis	Permanently discontinue
Hepatitis	Aspartate aminotransferase (AST)/or alanine aminotransferase (ALT) more than 3 and up to 5 times the upper limit of normal or total bilirubin more than 1.5 and up to 3 times the upper limit of normal	Withhold dose ^a
	AST or ALT more than 5 times the upper limit of normal or total bilirubin more than 3 times the upper limit of normal	Permanently discontinue
Hypophysitis	Grade 2 or 3 hypophysitis	Withhold dose ^a
	Grade 4 hypophysitis	Permanently discontinue
Adrenal insufficiency	Grade 2 adrenal insufficiency	Withhold dose ^a
	Grade 3 or 4 adrenal insufficiency	Permanently discontinue
Type 1 Diabetes Mellitus	Grade 3 hyperglycemia	Withhold dose ^a
	Grade 4 hyperglycemia	Permanently discontinue
Nephritis and renal dysfunction	Serum creatinine more than 1.5 and up to 6 times the upper limit of normal	Withhold dose ^a
	Serum creatinine more than 6 times the upper limit of normal	Permanently discontinue
Skin	Grade 3 rash or suspected Stevens-Johnson syndrome (SJS) or toxic epidermal necrolysis (TEN)	Withhold dose ^a
	Grade 4 rash or confirmed SJS or TEN	Permanently discontinue
Encephalitis	New-onset moderate or severe neurologic signs or symptoms	Withhold dose ^a
	Immune-mediated encephalitis	Permanently discontinue
Other	Other Grade 3 adverse reaction: 1. First occurrence 2. Recurrence of same Grade 3 adverse reactions	1. Withhold dose ^a 2. Permanently discontinue
	Life threatening or Grade 4 adverse reaction	Permanently discontinue

Columbia University Medical Center
Herbert Irving Comprehensive Cancer Center
Version Date: January 30, 2024

	Requirement for 10 mg per day or greater prednisone or equivalent for more than 12 weeks	Permanently discontinue
	Persistent Grade 2 or 3 adverse reactions lasting 12 weeks or longer	Permanently discontinue

*Toxicity was graded per National Cancer Institute Common Terminology Criteria for Adverse Events. Version 4.0 (NCI CTCAE v4).

^a Resume treatment when adverse reaction returns to Grade 0 or 1.

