8 TREATMENT PLAN

8.1 Agent Administration

Treatment will be preferentially administered on an outpatient basis. Reported adverse events and potential risks for nivolumab are described in Section 8.2. Appropriate dose modifications for nivolumab are described in Section 9. No investigational or commercial agents or therapies other than those described below may be administered with the intent to treat the participant’s malignancy.

Agent	Dose	Route	Schedule	Cycle Length
Nivolumab	240mg	IV over 30 minutes (± 7 minutes) infusion	Cycle 1-8	2 weeks (14 days)
	480mg		Cycle 9 – end of study	4 weeks (28 days)

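### The Section 9 hepatitis row leads to withhold and restart for a combined liver-test pattern that Section 8.5 and the resume criteria stop permanently, and its restart footnote leaves out the resume exceptions

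*Combined protocol and SAP*

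**What the plan says.** Four parts of the protocol govern liver-test elevations on nivolumab.

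- **Section 9, table of recommended dose modifications, hepatitis row.** The dose is withheld when AST or ALT is "more than 3 and up to 5 times the upper limit of normal or total bilirubin more than 1.5 and up to 3 times" that limit. Treatment stops permanently at "AST or ALT more than 5 times the upper limit of normal or total bilirubin more than 3 times the upper limit of normal". Footnote a, attached to every withhold entry, reads "Resume treatment when adverse reaction returns to Grade 0 or 1".
- **Section 8.5.** The list of reasons for permanent discontinuation includes "Concurrent AST or ALT > 3xULN and TBILI > 2xULN".
- **Section 9, Criteria to Resume Dosing (combined values).** "Participants with combined Grade 2 AST/ALT AND TBILI values meeting discontinuation parameters should have treatment permanently discontinued".
- **Section 9, Criteria to Resume Dosing (restart).** After a Grade 2 AST, ALT or bilirubin elevation, "dosing may resume when laboratory values return to baseline and management with corticosteroids, if needed, is complete". For other organs, "Drug-related pulmonary toxicity, diarrhea, or colitis must have resolved to baseline before treatment is resumed", with one exception for persistent Grade 1 pneumonitis after a steroid taper of at least one month.

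Section 8.1 directs sites as follows: "Appropriate dose modifications for nivolumab are described in Section 9". Section 6.9 makes discontinuation mandatory for unacceptable toxicity and refers to Section 8.5 for what that means.

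**The concern.** The hepatitis row joins its two laboratory conditions with 'or' and never addresses both being raised together. A participant with drug-related ALT of 4 × ULN and bilirubin of 2.5 × ULN is inside both withhold bands and below both stop lines. Read by itself, the row leads to withholding and then, through footnote a, to restart. Section 8.5 takes the same participant off drug for good.

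The footnote raises a second, separate question. It states the general restart rule without the exceptions that the resume criteria attach to it. A site working from the table could restart before liver tests are back to baseline or while steroids for the event are still being given.

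What is at stake is participant safety and consistent conduct across the three sites. A restart that follows the table would comply with one provision and breach another.

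**Working it through.** No sample-size or power figure is involved. The check compares rules. Write *a* for AST or ALT and *b* for total bilirubin, both in multiples of ULN.

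**1. Where the stop rules differ**

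- Section 8.5 concurrent rule: stop if *a* > 3 and *b* > 2.
- Table: stop if *a* > 5 or *b* > 3; otherwise withhold if 3 < *a* ≤ 5 or 1.5 < *b* ≤ 3.
- Stopped by Section 8.5 but not by the table: 3 < *a* ≤ 5 and 2 < *b* ≤ 3. Every point in that region is in the table's withhold band.

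| *a* | *b* | Table | Section 8.5 concurrent rule |
|---|---|---|---|
| 4 | 1.8 | withhold | not met |
| 4 | 2.0 | withhold | not met |
| 4 | 2.5 | withhold | stop (conflict) |
| 5 | 3.0 | withhold | stop (conflict) |
| 4 | 3.5 | stop | stop |
| 5.5 | 2.5 | stop | stop |

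At bilirubin of 2 × ULN or below, the concurrent rule is not met, and the table's withhold agrees with the Grade 2 delay rule. Above 5 × ULN for AST/ALT or 3 × ULN for bilirubin, the table stops as well.

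In Section 8.5 the concurrent line is nested under exceptions for Grade 3 laboratory abnormalities. Its thresholds nevertheless reach into the withhold band, and the resume criteria name combined Grade 2 values. The benefit/risk asterisk in Section 8.5 is attached to the preceding line on AST, ALT or bilirubin grade, not to the concurrent line.

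**2. How far the restart rules differ on grade**

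The protocol does not reproduce the grade boundaries. Assume that Grade 1 ends where the table's withhold band begins: 3.0 for AST/ALT and 1.5 for bilirubin. Then gap = Grade 1 ceiling − participant's baseline. A positive gap means that footnote a is looser than the resume criteria. Section 6.1 allows entry at AST/ALT up to 3.0 × ULN and bilirubin up to 1.5 × ULN, or below 3.0 × ULN with Gilbert syndrome.

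| Test | Baseline (× ULN) | Gap (× ULN) |
|---|---|---|
| AST/ALT | 1.0 | 3.0 − 1.0 = 2.0 |
| AST/ALT | 2.0 | 3.0 − 2.0 = 1.0 |
| AST/ALT | 3.0 | 3.0 − 3.0 = 0 |
| Bilirubin | 1.0 | 1.5 − 1.0 = 0.5 |
| Bilirubin | 1.5 | 1.5 − 1.5 = 0 |
| Bilirubin, Gilbert | 2.0 | 1.5 − 2.0 = −0.5 |

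The last line is negative, so for that participant footnote a is the stricter rule on grade. The missing steroid condition does not depend on baseline.

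**3. Rows affected**

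Footnote a appears in all 10 event rows: colitis, pneumonitis, hepatitis, hypophysitis, adrenal insufficiency, type 1 diabetes, nephritis, skin, encephalitis and other. For 3 of them (colitis, pneumonitis, hepatitis) the resume criteria set a specific return-to-baseline rule.

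**4. Effect of adding the concurrent line**

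The table would then stop if *a* > 5, or *b* > 3, or both *a* > 3 and *b* > 2. No point stopped by the Section 8.5 concurrent rule would remain in the withhold band.

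**The case against.** The other side has substantial points. Section 6.9 uses mandatory language and sends discontinuation to Section 8.5. Section 9 ties restart after a delay to the re-treatment criteria. The table is headed as recommended, and the correct rules stand directly above it. Section 8.1 refers to Section 9 as a whole, not to the table. Withholding is compatible with the resume criteria: hold the dose, then apply the rule that bars restart. Footnote a repeats the general rule, and its silence on steroids waives nothing. Section 10.10 also treats AT above 3 × ULN with bilirubin above 2 × ULN, without initial cholestasis or another apparent cause, as potential drug-induced liver injury to be reported as an SAE. SAE reports go to the manufacturer and the DSMC within 24 hours under Section 10.6.

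Most of this stands, and it limits the point. A reader might infer that the protocol lacks a stop rule for concurrent elevation, or gives no signal of which text binds. Neither is supported: two explicit rules stop the drug, and Section 6.9 points to one of them. A reader might also infer that footnote a is looser throughout. On grade it is not, as the raised-baseline and Gilbert cases show.

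What remains is the mismatch itself. The combined-value sentence in the resume criteria gives no thresholds and names no section. The only numeric liver stop lines in Section 9 are those in the table, and values inside the withhold bands cannot reach them. The sentence therefore works only for a reader who goes back to Section 8.5. SAE reporting makes an unnoticed restart less likely but does not bar one.

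**Conclusion.** Wrong as written, minor. The table disagrees with the protocol's own binding rules in one bounded region: AST/ALT above 3 and up to 5 × ULN with bilirubin above 2 and up to 3 × ULN. It also drops the restart conditions that apply to 3 of its 10 rows. On grade, the footnote is looser only when baseline lies below the Grade 1 ceiling, and it can be stricter in Gilbert syndrome. The size of that gap rests on the ceiling assumed in the working. The steroid omission applies at every baseline.

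The risk is limited to a site dosing from the table alone. The content of the Appendix 1 hepatic algorithm is not in the text available, so whether it carries a combined stop cannot be judged. The documents give no incidence of the pattern, so no count among the 37 participants is offered. A reader might infer that the response-rate result is affected. Nothing in the documents supports that, and it is not claimed.

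**What to change.** 1. Add a line to the hepatitis row: *AST or ALT >3 × ULN with concurrent total bilirubin >2 × ULN: permanently discontinue.* Leave the existing stop lines at 5 × and 3 × ULN unchanged.
2. Amend footnote a: *Resume when the adverse reaction returns to Grade 0 or 1, subject to the exceptions in Criteria to Resume Dosing (Grade 2 AST/ALT/TBILI: baseline and corticosteroid management complete; pulmonary toxicity, diarrhea or colitis: as stated there).*

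These two changes are sufficient for this point. If the sponsor also wants a precedence sentence, it should say that where Section 8.5, the resume criteria and the table differ, the more restrictive rule applies. It should not be confined to the liver rules, because that would imply that the table governs elsewhere. Grade 3 drug-related colitis lasting more than 7 days shows the danger: Section 8.5 stops it permanently, while the table withholds and restarts.

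The cost is one table line and one reworded footnote, using rules already in the protocol. No tests, visits or staff are added.
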